stratum will be used and stratification will be based on baseline A1C (i.e., $\geq 9\%$ or $< 9\%$), site (i.e., CCHMC, the University of Colorado Barbara Davis Center or the University of Florida), and Barriers to Diabetes Adherence elevation type within the treatment arm (i.e., elevated on one or both of the subscales). The A1C criterion was selected because the average A1C in 13-17 year olds with T1D in the US is 9%, which will result in comparable sample sizes above and below 9%. In addition, although the American Diabetes Association recommends an A1C $< 7\%$, very few adolescents achieve this. Site was chosen as a stratification variable to ensure balance for any site-related differences. This randomization strategy will minimize imbalance of the number of participants across groups. The randomization list will be held by an individual independent of the study to reduce any potential biases. Participants will be notified of their randomization group within 3 business days of completion of baseline data and be provided with appropriate materials (e.g., log-in information or website information and links). Total treatment time is up to 12 weeks, which coincides with routine quarterly T1D clinic appointments. This also enables sufficient time for cancelled and/or rescheduled sessions that are likely to occur given adolescents' busy schedules.

Control Group (Enhanced Standard of Care)

Participants randomized to Enhanced Standard of Care will receive general education via the T1DToolkit website, as well as 4 Zoom sessions (e.g., Zoom for Healthcare; See Appendix C) with certified diabetes educators (CDEs) from either CCHMC or UF across 12-weeks. Notably, if technical difficulties arise, telephone sessions will be conducted and audio recorded. Content to address adherence barriers were modified and or newly developed for the Enhanced Standard of Care group via the T1DToolkit website. Depending on the participant's elevated score(s) on the Barriers to Diabetes Adherence scale, patients will receive information specifically addressing elevated scales of the BDA. Treatment fidelity will be assessed via audio recordings and completion of checklists, which will be reviewed weekly by [name] with the CDEs who deliver this intervention.

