number, and password protected to ensure privacy. A medical chart review will also be conducted to gather information about hemoglobin A1C, data downloaded from devices, medications, comorbidities, hospitalizations, and time since diagnosis.

It is the goal for all participant families to complete their baseline visit prior to being randomized to intervention. This will include completion of questionnaires and download data from their T1D device. However, participating families may be randomized if the primary outcome measure (BDA) and a baseline A1C within 4 weeks of enrollment is available, at a minimum. Participants will have an opportunity to complete baseline questionnaires until the initiation of the first intervention session. Device downloads will not be required for randomization as these data can be retrieved from the medical record.

After completion of the required questionnaires and A1C at a minimum will be randomized to either: Diabetes Journey or Enhanced Standard of Care (Figure 1). Stratified block randomization with two strata and blocks of size 2 or 4 chosen randomly within each

Modules	T1Dtoolkit.com links
Stress and Burnout	
Burnout	https://t1dtoolkit.org/for-teens-young-adults/burnout-2/
Sharing responsibility	https://t1dtoolkit.org/for-teens-young-adults/sharing-responsibility/
Strategies to Manage Pain	https://t1dtoolkit.org/uncategorized/strategies-to-manage-pain/
Building a Support Network	https://t1dtoolkit.org/uncategorized/building-a-support-network/
Time Pressure and Planning	
Setting Reminders	https://t1dtoolkit.org/for-teens-young-adults/setting-reminders/
Prioritizing and Planning	https://t1dtoolkit.org/for-teens-young-adults/14472/
Organization of Your Environment	https://t1dtoolkit.org/for-teens-young-adults/organizing-your-environment/
Eating on Your Own	https://t1dtoolkit.org/for-teens-young-adults/eating-on-your-own/

Treatment (Diabetes Journey)

[figure not shown]

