Given recruitment challenges and the resulting changes to eligibility and randomization, we decided to focus on the overall *Diabetes Journey* versus Enhanced Standard of Care difference at our primary endpoint, instead of powering for treatment subgroup comparisons. Using the same effect size estimates and assumptions in the original power analyses, but assuming a 1:1 randomization to only two groups, we determined that reducing the sample size from $N = 256$ to $N = 190$ ensured $>80\%$ power to detect a follow-up group difference effect size of $\Delta d = 0.36$, resulting in final group sizes of $n = 110$ in *Diabetes Journey* and $n = 80$ in Enhanced Standard of Care.

Randomization

At baseline, all participants who met inclusion/exclusion criteria (e.g., elevations on the Stress/Burnout and/or Time Pressure/Planning subscales of the Barriers to Diabetes Adherence questionnaire) were randomized to either the control group (i.e., Enhanced Standard of Care) or treatment group (i.e., *Diabetes Journey*). We used stratified block randomization with two strata and blocks of size 2 or 4 chosen randomly within each stratum. Stratification was based on baseline HbA1c (i.e., $>9\%$ or $<9\%$), site (i.e., CCHMC or University of Florida/University of

Colorado's Barbara Davis Center for Diabetes), and Barriers to Diabetes Adherence elevation type within the treatment arm (i.e., elevated on one or both of the subscales). The HbA1c criterion was selected because the average HbA1c in 13-17 year olds with T1D in the US is 9%, which resulted in comparable sample sizes above and below 9%. In addition, although the American Diabetes Association recommends an HbA1c <7%, very few adolescents achieve this. Site was chosen to ensure balance for any site-related differences. The randomization list was held by an individual independent of the study to reduce any potential biases. Those who were randomized were notified of their randomization status after completion of the baseline questionnaires so intervention materials could be provided immediately.

Measures

Definitions and Derivations (numbers at the end of variable names represent timepoint: 0=baseline; 1=post-treatment, 2=follow-up1 and 3=follow-up2)

Barriers to Diabetes Adherence (BDA) (Mulvey et al., 2011)				
Subscale	Descriptor	Items	Range	Interpretation
bdastress	BDA Stress and Burnout Subscale	4	1-5	↑ scores ↑ stress and burnout

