An intent to treat approach will be undertaken for all analyses. We will examine the data for intervention group comparability using chi-square tests for categorical variables (e.g., biological sex, insurance status, technology use) and t-tests for continuous variables (e.g., age, T1D duration) prior to analysis of the primary outcomes. Should we observe intervention group

differences at baseline on any variables, these variables will be added to the outcome models as covariates.

Our primary hypothesis examines group differences at the 6-month follow-up (i.e., primary end point) given that we expect participants to have made the most significant gains from the intervention after implementing the acquired skills for some time. Two separate Analysis of Covariance models (one for each barrier subscale) will be used to test the primary hypothesis that the *Diabetes Journey* intervention group will demonstrate significantly lower barriers compared to the Enhanced Standard of Care group at 6-month follow-up, after controlling for baseline barriers. For secondary outcomes (i.e., HRQOL, T1D self-management behaviors, HbA1c), the same analytical approach will be used, with baseline values of the respective outcome included as a covariate. To evaluate the treatment effect on our primary and secondary outcomes across time, we will employ Generalized Estimating Equations (GEE), while controlling for baseline covariates.

Handling Missing Data

Missing data will be addressed using full information maximum likelihood (FIML) under the assumption of data missing at random (MAR) in the ANCOVA models. For the longitudinal GEE models, we will use multiple imputation to address missing data under the assumption that the data are Missing at Random (MAR). The imputation will use chained equations (mi impute chained) with relevant predictors to generate 100 imputed datasets.

Variables:

Outcome variables:

- Primary: BDA subscale scores for stress and time pressure (bdastress, bdatime)
- Secondary: alc, T1DAL subscales and total score (t1dalhandlingt1d, t1daltpeer, t1daltfamily, t1dalemotionr, t1daltotalr)
- **Group (independent variable):**
 - condition (0 = ESC, 1 = DJ)
- **Timepoints:**
 - time (post-treatment = 1, follow-up 1 = 2, follow-up 2 = 3)
- **Covariates:**
 - age (continuous)
 - sex (categorical, 0 = male, 1 = female)
 - insurance (insur, 0=public, 1=private)
 - time since dx (timedx, continuous)
 - use of technology (cgm yes = 1, cgm no = 0)

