 - adolescent reported COVID impact scores at baseline (cefisaya_impact; continuous)
 - baseline outcome scores (outcome scores measured at time 0; continuous)
 - site (dummy coded as s1, s2; UF, BDC, CCHMC)
- **Correlation Structure (for GEE model):** Exchangeable correlation structure (to account for correlations within participants over time).

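### The A1C randomisation stratum is missing from both primary barrier models, and the baseline test-and-add rule leaves those models open without being able to restore it

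*SAP*

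**What the plan says.** **Randomisation.** The SAP (Randomization) states "Stratification was based on baseline HbA1c", split at 9%, together with site and "Barriers to Diabetes Adherence elevation type within the treatment arm (i.e., elevated on one or both of the subscales". The protocol (section 8, Study Procedures) agrees that "stratification will be based on baseline A1C", and names the same three factors. Blocks are of size 2 or 4 within strata.

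**Primary model.** The SAP (Primary Aim Analysis Plan) sets one ANCOVA per barrier subscale at 6 months, "after controlling for baseline barriers". No other covariate is named in that sentence.

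**Covariate list.** The Variables block that follows lists age, sex, insurance, time since diagnosis, CGM use, adolescent COVID impact, the baseline value of the outcome being modelled, and "site (dummy coded as s1, s2; UF, BDC, CCHMC". Site is therefore the only stratification factor listed as such. Baseline A1C enters only the HbA1c model, as that outcome's own baseline.

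**Test-and-add rule.** Arms are compared at baseline with chi-square and t-tests. Should the comparison show "differences at baseline on any variables, these variables will be added to the outcome models as covariates". The tested variables are given only as examples, and no significance level is stated.

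**The concern.** A factor used to stratify the randomisation belongs in the analysis model. Balancing a prognostic factor reduces the true variability of the treatment estimate. A model without that factor still counts its variance as residual error, so the reported standard error is too large and the test is conservative.

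The test-and-add rule does not repair this. Under randomisation, baseline differences arise by chance, and a test for them does not measure how well a variable predicts the outcome. A factor balanced by design is the least likely to be flagged. The rule can let in unimportant variables while keeping A1C out, and it leaves the primary covariate set undecided until the baseline tests have been run.

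Two further points are unclear. The ANCOVA sentence names only baseline barriers, so the covariate list may or may not apply to it. Elevation type is described as a factor within the treatment arm, so it may not have balanced the arms. It is also absent from the models, and each model's own baseline subscale captures it only in part.

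**Working it through.** **Inputs from the documents.** N = 190 (95/95 in the protocol, 110/80 in the SAP); difference 0.55 − 0.19 = 0.36; R² = 0.30; attrition 25%. Assumed, because the SAP is silent: two-sided 5% level, independent baseline tests, and the extra variance explained by the omitted factors.

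**1. The plan's own power figure.** The SAP states more than 80% at N = 190. With residual SD √0.70 = 0.837 and a normal approximation, power is Φ(0.36/SE − 1.96), where SE = 0.837 × √(1/n₁ + 1/n₂).

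| Case | Power |
|---|---|
| 95/95, 25% attrition, two-sided | 72.9% |
| 110/80, 25% attrition, two-sided | 71.8% |
| 95/95, no attrition, two-sided | 84.3% |
| 95/95, 25% attrition, one-sided | 82.2% |

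The stated figure is met one-sided or without attrition, but not two-sided with the stated attrition. FIML using the 3-month score could recover part of the gap. The concern does not depend on this figure, but it means there is little precision to spare.

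**2. Power from including the omitted factors.** Noncentral t, two-sided 5%, d = 0.36, after 25% attrition (95 × 0.75 = 71.25; 110 × 0.75 = 82.5; 80 × 0.75 = 60):

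| R² | 71.25 + 71.25 | 82.5 + 60 |
|---|---|---|
| 0.30 | 72.3% | 71.2% |
| 0.32 | 73.5% | 72.4% |
| 0.35 | 75.4% | 74.3% |

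The standard error ratios are √(0.68/0.70) = 0.986 and √(0.65/0.70) = 0.964, a reduction of 1.4% to 3.6%.

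Simulation agrees (N = 190, blocks of 2 or 4 within A1C × site, 25% missing at random, 4,000 trials per cell, A1C adding 2 or 5 points):

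| | A1C omitted | A1C included |
|---|---|---|
| Mean reported SE | 0.140–0.141 | 0.136–0.139 |
| Null rejection | 4.1–4.4% | 4.4–5.1% |
| Power | 72.5–72.8% | 73.9–75.3% |

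With A1C omitted, the empirical SD of the estimate was 0.135–0.138, below the mean reported SE.

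The extremes bound the gain. With no A1C effect the two models had the same power (71.1%). The protocol (Background) gives a correlation of 0.38 between barriers and glycaemic levels. Taking 0.38² = 0.144 as a generous ceiling, power was 72.1% without the stratum and 80.6% with it. That correlation is crude and takes no account of the baseline subscale, so the true gain should be well below this.

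**3. Can the rule restore A1C?** A 5% chi-square test flagged the A1C stratum in 0 of 56,000 simulated stratified-block trials (2 or 3 site groups, with or without elevation type in the strata). A separate run of 32,000 trials also gave 0; there a t-test on continuous A1C fired in 0.1–0.2%. Under simple randomisation the two rates were 4.9% and 5.2%. Elevation type was flagged in 4.5–4.7% of trials if it did not balance the arms and in 0% if it did.

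**4. What the rule does admit.** Seven baseline variables defined in the SAP lie outside the covariate list: race, ethnicity, caregiver relationship, marital status, education, insulin method and COVID distress. If the list is for the GEE only, age, sex, insurance, time since diagnosis, CGM and COVID impact are also open, making 13.

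- 7 open: 1 − 0.95⁷ = 0.302
- 13 open: 1 − 0.95¹³ = 0.487

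**5. Effect on the primary verdict.** With each open variable explaining 1–2% of variance (assumed; 8,000 trials per cell), screening changed the significance verdict in 0.9–2.1% of null trials and in 2.8–5.9% at d = 0.36. Null rejection with screening was 4.1–5.1%.

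**The case against.** The strongest reply is that little is lost. This is a pilot, the linear estimate is unbiased, type I error is not inflated, and the documents give no figure for what A1C adds beyond the baseline subscale. At 0.5 to 1 extra point of variance, power moves only from 72.3% to 72.6–72.9%. This stands, and it limits the grade of the concern rather than removing it.

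The SAP also places the baseline comparison before the primary outcome analysis, so the covariate choice depends on baseline data and not on results. That is a real safeguard. The model is still not fixed in advance, because neither the threshold nor the set of tested variables is stated.

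The admission figures can be disputed. All five variables the SAP gives as testing examples are already in its list, and it never says that all seven others will be tested. The list probably does apply to the ANCOVA, since only the correlation structure is labelled as being for the GEE; 30% therefore deserves more weight than 49%. With an assumed correlation of 0.3 between test statistics the figures fall to 27% and 42%; if further baseline scores are tested they rise. The top verdict case, 13 variables at 2% each, amounts to 26% of variance, close to the whole planned R² of 0.30.

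Finally, allocation was not 1:1 throughout: the SAP reports a return to 1:1 and final groups of 110/80. Simulations with an assumed early 2:1 period averaging 110 in the treatment arm, and A1C prevalence shifting by 0, 10 or 20 points between periods, flagged the A1C stratum in 0 of 15,000 trials. The objection does not rescue the rule.

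**Conclusion.** The concern holds. Baseline A1C is a stratification factor in both documents and is absent from both primary barrier models, whether or not the covariate list applies to the ANCOVA. The test-and-add rule has no threshold or closed list and cannot be expected to bring A1C back.

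The consequence is mild: a slightly conservative test, about 1 to 3 points of power lost if the omitted factors explain a further 2 to 5 points of variance, and a primary covariate set that is not fully pre-specified. The power range is assumed; the gain is nil if A1C adds nothing beyond the baseline subscale. The admission probabilities rest on a 5% level and independence. For elevation type, the conservative-test argument applies only if it was balanced across arms. This should be corrected, but it does not threaten the trial's validity.

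**What to change.** Delete the test-and-add rule and report baseline balance descriptively. Pre-specify one primary ANCOVA per subscale: 6-month score on condition, baseline subscale, A1C stratum, site, elevation type (one subscale or both) and the covariates already listed. State that this list governs the ANCOVA. Use the same terms in the secondary ANCOVAs and the GEE; baseline A1C already enters the HbA1c model. Elevation type is fixed before randomisation, so including it is harmless even if it did not balance the arms.

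Take the strata from the randomisation list as used. State whether elevation type was balanced across arms, and reconcile the documents on three points: site levels (three in the protocol, two in the SAP's Randomization section), the stratum for an A1C of exactly 9% (upper in the protocol, unassigned in the SAP), and the description of two strata for three factors.

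The cost is SAP wording and two binary covariates. Because the SAP already reports conduct and final group sizes, the change should be dated and justified, and should say whether outcome data by arm had been seen. The data should exist: the protocol allows randomisation if the BDA and "a baseline A1C within 4 weeks of enrollment is available, at a minimum". The SAP's Introduction, however, names the BDA as the only measure required before randomisation, so check the list for anyone stratified without an A1C.
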